A mixed effect model will be fitted to the 9-point profile data. The model will include treatment, previous OAD treatment, time, interaction between treatment and time, and interaction between previous OAD treatment and time as fixed factors, and subject as random effect, where measurements within subjects will be assumed correlated with a compound symmetry covariance matrix. From the model mean profile by treatment and relevant treatment differences will be estimated and explored.

Change from baseline after 26 weeks of treatment in mean of the 9-point profile and post-prandial increment endpoints will be analysed separately using the standard ANCOVA model.

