3 Changes to the statistical analyses planned in the protocol

- Additional sensitivity analysis was added, using the pattern mixture model, in order to evaluate the sensitivity of using LOCF for primary endpoint, change from baseline in HbA_{1c} after 26 weeks of treatment.
- Sensitivity analyses for confirmatory secondary endpoint, change from baseline in body weight after 26 weeks of treatment, were added to evaluate the sensitivity of using LOCF.

- Sensitivity analysis for confirmatory secondary endpoint, number of treatment emergent severe or BG confirmed hypoglycaemic episodes during 26 weeks of treatment, was added to evaluate the sensitivity of the analysis specified in the protocol.
- A minor correction regarding the analysis model for the supportive secondary endpoint of 9-point self-measured plasma glucose was made (baseline value was removed from the model and interaction between previous OAD and time was added).
- Box plots will only be presented for relevant laboratory assessments: lipase, amylase and calcitonin.
- Listings deemed unnecessary were removed: antibody measurements, physical examination findings.
- Minor editorial changes were made, and clarifications were added where considered relevant.

4 References

1. Food and Drug Administration, CDER. Guidance for Industry. Diabetes Mellitus: Developing Drugs and Therapeutic Biologics for Treatment and Prevention, Draft Guidance. February 2008.
2. ICH Harmonised Tripartite Guideline. Statistical Principles for Clinical Trials E9, Current Step 4 version. 05 Feb 1998.

Table of contents

| | Page |
|--|-------------|
| 1: Actual daily total insulin dose after 26 weeks of treatment - supportive statistical analysis - full analysis set..... | 3 |

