| trtpn | LSMeans, Lira | 7.7261 | 8.2080 | 2884.34 | 2266.80 | 3670.11 |

Least Squares Means Estimates

| Effect | Label | Margins | Estimate | Standard Error | DF | t Value |
|--------|-------------------------------------|-------------|----------|----------------|-----|---------|
| trtpn | Treatment contrast, IDegLira - IDeg | WORK.ADATA2 | -0.4651 | 0.1510 | 713 | -3.08 |

Least Squares Means Estimates

| Effect | Label | Pr > t | Alpha | Lower | Upper | Exponentiated |
|--------|-------------------------------------|---------|-------|---------|---------|---------------|
| trtpn | Treatment contrast, IDegLira - IDeg | 0.0021 | 0.05 | -0.7615 | -0.1687 | 0.6281 |

Least Squares Means Estimates

| Effect | Label | Exponentiated Lower | Exponentiated Upper |
|--------|-------------------------------------|---------------------|---------------------|
| trtpn | Treatment contrast, IDegLira - IDeg | 0.4670 | 0.8447 |

Fasting plasma glucose after 26 weeks of treatment - change from baseline - supportive statistical analysis - full analysis set

Parameter Code=C105585P

The Mixed Procedure

Least Squares Means Estimates

| Effect | Label | Margins | Estimate | Standard Error | DF | t Value |
|--------|-------------------------------------|-------------|----------|----------------|-----|---------|
| trtpn | Treatment contrast, IDegLira - Lira | WORK.ADATA2 | -1.8662 | 0.1503 | 713 | -12.42 |

Least Squares Means Estimates

| Effect | Label | Pr > t | Alpha | Lower | Upper | Exponentiated |
|--------|-------------------------------------|---------|-------|---------|---------|---------------|
| trtpn | Treatment contrast, IDegLira - Lira | <.0001 | 0.05 | -2.1612 | -1.5712 | 0.1547 |

Least Squares Means Estimates

| Effect | Label | Exponentiated Lower | Exponentiated Upper |
|--------|-------------------------------------|---------------------|---------------------|
| trtpn | Treatment contrast, IDegLira - Lira | 0.1152 | 0.2078 |

Fasting plasma glucose after 26 weeks of treatment - change from baseline - supportive statistical analysis - full analysis set

Parameter Code=FPGU

The Mixed Procedure

Model Information

| | |
|---------------------------|-------------|
| Data Set | WORK.ADATA2 |
| Dependent Variable | AVAL |
| Covariance Structure | Diagonal |
| Estimation Method | REML |
| Residual Variance Method | Profile |
| Fixed Effects SE Method | Model-Based |
| Degrees of Freedom Method | Residual |

Class Level Information

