| trtpn | Change from baseline, IDegLira | WORK.ADATA2 | -63.9010 | 1.5634 | 713 | -40.87 | <.0001 |
| trtpn | Change from baseline, IDeg | WORK.ADATA2 | -55.5197 | 2.2253 | 713 | -24.95 | <.0001 |
| trtpn | Change from baseline, Lira | WORK.ADATA2 | -30.2715 | 2.2113 | 713 | -13.69 | <.0001 |

Least Squares Means Estimates

| Effect | Label | Alpha | Lower | Upper |
|--------|--------------------------------|-------|----------|----------|
| trtpn | Change from baseline, IDegLira | 0.05 | -66.9703 | -60.8317 |
| trtpn | Change from baseline, IDeg | 0.05 | -59.8887 | -51.1508 |
| trtpn | Change from baseline, Lira | 0.05 | -34.6130 | -25.9300 |

19: 9-point self-measured plasma glucose profile after 26 weeks of treatment - supportive statistical analysis - full analysis set

Parameter Code=C105585Y

The Mixed Procedure

Model Information

| | |
|---------------------------|-------------------|
| Data Set | WORK.ANA_DATA |
| Dependent Variable | AVAL |
| Covariance Structure | Compound Symmetry |
| Subject Effect | USUBJID |
| Estimation Method | REML |
| Residual Variance Method | Profile |
| Fixed Effects SE Method | Kenward-Roger |
| Degrees of Freedom Method | Kenward-Roger |

9-point self-measured plasma glucose profile after 26 weeks of treatment - supportive statistical analysis - full analysis set

Parameter Code=C105585Y

The Mixed Procedure

Number of Observations

Number of Observations Read 6480
 Number of Observations Used 6401
 Number of Observations Not Used 79

Iteration History

| Iteration | Evaluations | -2 Res Log Like | Criterion |
|-----------|-------------|-----------------|------------|
| 0 | 1 | 28226.72908143 | |
| 1 | 2 | 26184.01976519 | 0.00000000 |

Convergence criteria met.

Covariance Parameter Estimates

| Cov Parm | Subject | Estimate | Standard Error | Z Value | Pr > Z | Alpha | Lower | Upper |
|----------|---------|----------|----------------|---------|--------|-------|--------|--------|
| CS | USUBJID | 2.0262 | 0.1238 | 16.37 | <.0001 | 0.05 | 1.7835 | 2.2688 |
| Residual | | 2.7716 | 0.05215 | 53.15 | <.0001 | 0.05 | 2.6721 | 2.8767 |

Asymptotic Covariance Matrix of Estimates

| Row | Cov Parm | CovP1 | CovP2 |
|-----|----------|----------|----------|
| 1 | CS | 0.01533 | -0.00031 |
| 2 | Residual | -0.00031 | 0.002720 |

Fit Statistics

-2 Res Log Likelihood 26184.0
 AIC (Smaller is Better) 26188.0
 AICC (Smaller is Better) 26188.0
 BIC (Smaller is Better) 26197.2

Null Model Likelihood Ratio Test

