| Effect | Planned Treatment for Period 01 (N) | Analysis Timepoint (N) | Alpha | Lower | Upper |
|---------------|-------------------------------------|------------------------|-------|---------|---------|
| TRTPN (ATPTN) | 1 | 1 | 0.05 | 5.3565 | 5.8086 |
| TRTPN (ATPTN) | 2 | 1 | 0.05 | 5.5730 | 6.2151 |
| TRTPN (ATPTN) | 3 | 1 | 0.05 | 6.8497 | 7.4900 |
| TRTPN (ATPTN) | 1 | 2 | 0.05 | 8.8898 | 9.3428 |
| TRTPN (ATPTN) | 2 | 2 | 0.05 | 9.6493 | 10.2963 |
| TRTPN (ATPTN) | 3 | 2 | 0.05 | 10.0746 | 10.7172 |
| TRTPN (ATPTN) | 1 | 3 | 0.05 | 6.2844 | 6.7387 |
| TRTPN (ATPTN) | 2 | 3 | 0.05 | 6.9483 | 7.5942 |
| TRTPN (ATPTN) | 3 | 3 | 0.05 | 7.5982 | 8.2384 |
| TRTPN (ATPTN) | 1 | 4 | 0.05 | 8.8026 | 9.2564 |
| TRTPN (ATPTN) | 2 | 4 | 0.05 | 10.0335 | 10.6806 |
| TRTPN (ATPTN) | 3 | 4 | 0.05 | 9.5962 | 10.2377 |
| TRTPN (ATPTN) | 1 | 5 | 0.05 | 6.3966 | 6.8500 |
| TRTPN (ATPTN) | 2 | 5 | 0.05 | 7.2136 | 7.8571 |
| TRTPN (ATPTN) | 3 | 5 | 0.05 | 7.5594 | 8.1997 |
| TRTPN (ATPTN) | 1 | 6 | 0.05 | 9.1269 | 9.5815 |
| TRTPN (ATPTN) | 2 | 6 | 0.05 | 10.0928 | 10.7362 |
| TRTPN (ATPTN) | 3 | 6 | 0.05 | 9.5320 | 10.1722 |
| TRTPN (ATPTN) | 1 | 7 | 0.05 | 7.8827 | 8.3386 |
| TRTPN (ATPTN) | 2 | 7 | 0.05 | 8.6449 | 9.2931 |
| TRTPN (ATPTN) | 3 | 7 | 0.05 | 8.4840 | 9.1254 |
| TRTPN (ATPTN) | 1 | 8 | 0.05 | 5.5083 | 5.9660 |
| TRTPN (ATPTN) | 2 | 8 | 0.05 | 5.9636 | 6.6142 |

9-point self-measured plasma glucose profile after 26 weeks of treatment - supportive statistical analysis - full analysis set

Parameter Code=C105585Y

The Mixed Procedure

Least Squares Means

| Effect | Planned Treatment for Period 01 (N) | Analysis Timepoint (N) | Alpha | Lower | Upper |
|---------------|-------------------------------------|------------------------|-------|--------|--------|
| TRTPN (ATPTN) | 3 | 8 | 0.05 | 6.8466 | 7.4915 |
| TRTPN (ATPTN) | 1 | 9 | 0.05 | 5.2795 | 5.7324 |
| TRTPN (ATPTN) | 2 | 9 | 0.05 | 5.3804 | 6.0225 |
| TRTPN (ATPTN) | 3 | 9 | 0.05 | 6.7916 | 7.4342 |

Differences of Least Squares Means

| Effect | Planned Treatment for Period 01 (N) | Analysis Timepoint (N) | Planned Treatment for Period 01 (N) | Analysis Timepoint (N) | Margins | Estimate | Standard Error | DF |
|---------------|-------------------------------------|------------------------|-------------------------------------|------------------------|---------------|----------|----------------|------|
| TRTPN (ATPTN) | 1 | 1 | 2 | 1 | WORK.ANA_DATA | -0.3115 | 0.2002 | 2641 |

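### The 9-point glucose profile model forces one variance on fasting and post-meal points and leaves out the collected baseline, so its time-point standard errors are valid only if the nine variances are equal.

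*SAP*

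**What the plan says.** SAP section 2.4.2.1 (self-measured plasma glucose 9-point profile) specifies a mixed model with "subject as random effect, where measurements within subjects will be assumed correlated with a compound symmetry covariance matrix". Besides the main effects of treatment, previous OAD and time, it lists "interaction between treatment and time, and interaction between previous OAD treatment and time as fixed factors". No baseline term appears. The stated use is: "From the model mean profile by treatment and relevant treatment differences will be estimated and explored".

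Section 3 records how this departs from the protocol: "baseline value was removed from the model and interaction between previous OAD and time was added". It classes the change as a minor correction and gives no statistical reason.

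A baseline profile was collected. The same section sends "Change from baseline after 26 weeks of treatment in mean of the 9-point profile and post-prandial increment endpoints" to the standard ANCOVA, which section 2 defines with the corresponding baseline value as covariate. For repeated HbA1c measurements, section 2.3.1 specifies an unstructured covariance matrix.

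**The concern.** Compound symmetry has two parameters: one variance shared by all nine points and one correlation shared by all pairs. The profile runs from fasting or night values to values 90 minutes after meals, where both the level and the spread of glucose may differ. The IDegLira means in output 19 of the attached statistical documentation range from 5.51 to 9.35 mmol/L.

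A pooled variance is an average. If the true variances differ, it is too large at some points and too small at others, and so is every time-point standard error built on it. The Kenward-Roger method used in output 19 does not repair a misspecified covariance. What is at stake is the confidence interval and p-value attached to each time-point treatment difference.

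Leaving out baseline is a separate and smaller matter. It gives up some precision that the companion analyses of the same profile retain.

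**Working it through.** **Inputs (attached statistical documentation)**
- Output 19, covariance estimates: between-subject part "CS | USUBJID | 2.0262 | 0.1238 | 16.37" (estimate, its SE, z value), so 2.0262; residual 2.7716. Records used: 6,401 of 6,480.
- Output 19, IDegLira minus IDeg at time point 1: "WORK.ANA_DATA | -0.3115 | 0.2002 | 2641", so SE 0.2002.
- Output 18, fasting plasma glucose (FPG): residual variance 2.7090; F for baseline 21.29 on 1 and 713 df; "Treatment contrast, IDegLira - IDeg | WORK.ADATA2 | -0.4651 | 0.1510 | 713", so SE 0.1510.
- Output 2, HbA1c: F for baseline 95.66 on 1 and 715 df.

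**Step 1. Reproduce the printed standard error**
- Common variance: 2.0262 + 2.7716 = 4.7978 (SD 2.19; correlation 2.0262/4.7978 = 0.42).
- Arm sizes implied by the LS-mean SEs at point 1: 4.7978/0.1153² = 361 (IDegLira) and 4.7978/0.1637² = 179 (IDeg).
- SE of the difference: sqrt(4.7978 × (1/361 + 1/179)) = 0.2002, as printed.

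The model therefore applies 4.80 at every point. Accordingly, the nine IDegLira LS-mean SEs span only 0.1153 to 0.1167.

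**Step 2. Compare with fasting glucose**
- FPG residual variance is 2.71 after baseline adjustment. Partial R² for baseline is 21.29/(21.29 + 713) = 0.029, so the unadjusted variance is about 2.709/(1 − 0.029) = 2.79.
- SE at variance 2.79: sqrt(2.79 × (1/361 + 1/179)) = 0.1527. Ratio 0.2002/0.1527 = 1.31.
- The direct ratio 0.2002/0.1510 = 1.33 also contains the effect of baseline adjustment, so 1.31 is the cleaner comparison.

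**Step 3. Range of error under stated assumptions**

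Almost all records are used, so treat 4.7978 as the average of nine variances. Let five points (1, 3, 5, 8 and 9, which have the lower means) have variance v. The other four then average (9 × 4.7978 − 5v)/4. True SE = sqrt(variance × (1/361 + 1/179)). Coverage = 2Φ(1.96 × 0.2002/true SE) − 1.

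| Assumed v at five points | Variance at other four | SE, low / high points | Model SE at low points | Model SE at high points | Coverage of nominal 95%, low / high |
|---|---|---|---|---|---|
| 4.80 (equal) | 4.80 | 0.200 / 0.200 | correct | correct | 95% / 95% |
| 4.0 | 5.80 | 0.183 / 0.220 | 9.5% too large | 9.0% too small | 96.8% / 92.5% |
| 2.79 (FPG-like) | 7.31 | 0.153 / 0.247 | 31% too large | 19% too small | 99% / 89% |

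A simulation of 2,000 trials under the last row gave coverage of 98.9% and 88.6%; with equal variances it stayed near 95%.

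The split also matters. With variance 2.79 at three, four or six points instead of five, the SE at the remaining points is 9%, 13% or 26% too small, from 1 − sqrt(4.7978/((9 × 4.7978 − 2.79k)/(9 − k))) with k = 3, 4, 6.

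**Step 4. Cost of omitting baseline**
- FPG analogue: sqrt(1 − 0.029) = 0.985, so the SE falls 1.5%, from 0.2002 to 0.197.
- HbA1c analogue: partial R² = 95.66/(95.66 + 715) = 0.118; sqrt(1 − 0.118) = 0.939, so the SE falls 6.1%, to 0.188.

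**The case against.** The strongest reply is that unequal variance is not demonstrated. A reader might infer from the output that the error bars are wrong in both directions. The documents do not support that. They give no profile variance at any time point, and the near-identical printed SEs are no evidence, because compound symmetry produces them whatever the true variances are.

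The FPG comparison is also only a proxy. FPG is a laboratory value and the profile is self-measured. Their IDegLira means differ (6.10 for FPG, 5.58 at time point 1), so their variances may differ too. The shown text does not define the numbered time points; which are fasting or post-meal is read from the means. All of this stands, and it is why the size is given as a range that starts at zero.

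A reader might also note that the time-point-1 difference (printed p = 0.12) would look stronger with a smaller SE. That is no reason to change the model: a covariance structure should not be chosen by its effect on an observed p-value.

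On baseline, the reply is largely right. Omitting it does not bias a randomised comparison, the removal is openly declared, and the profile mean and meal increments already have baseline-adjusted analyses. What remains is a small loss of precision and a missing reason.

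Finally, the analysis is supportive and exploratory. Only 79 of 6,480 records are unused, so the estimated differences hardly depend on the covariance structure.

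**Conclusion.** The point holds in conditional form. The plan imposes a single variance where unequal variances are likely, and the time-point SEs, intervals and p-values are reliable only if that restriction is true. The error in the SE is none if variances are equal, about 9% each way with variances of 4.0 and 5.8, and about 31% too large and 19% too small if five points vary like laboratory FPG. The last two figures assume a five-to-four split of points and a pooled variance that averages the nine.

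Leaving out the baseline profile costs roughly 1.5 to 6% of the SE, on the assumption that baseline predicts the profile about as well as it predicts FPG or HbA1c.

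Point estimates barely change. The baseline-adjusted analyses of the profile mean and increments, the primary endpoint and the confirmatory endpoints are untouched.

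**What to change.** In section 2.4.2.1, replace compound symmetry by an unstructured within-subject covariance over the nine time points, and name heterogeneous compound symmetry as the fallback if the model does not converge. Add the baseline glucose value at the same time point as a covariate, with a baseline-by-time interaction. If baseline is to stay out, section 3 should state why.

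The unstructured matrix has 9 × 10/2 = 45 parameters, against two now, for 720 subjects and about 6,400 records. The SAP already uses this structure for its HbA1c MMRM, which converged. It gives appropriate time-point SEs whether or not the variances differ.

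The cost is two changes to the model statement and a sentence or two in the SAP, with no new data. The small downsides are the extra covariance parameters and the need to apply to subjects without a baseline profile the same baseline rule as in the companion ANCOVAs. Because results from the current model are already attached, a rerun should be labelled as an additional analysis.

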2.4.2.2 Safety endpoints

Adverse events

AEs will be coded using the most recent version of the Medical Dictionary for Regulatory Activities (MedDRA) coding.

A treatment emergent adverse event (TEAE) is defined as an event that has onset date on or after the first day of exposure to randomised treatment and no later than seven days after the last day of randomised treatment. If the event has onset date before the first day of exposure on randomised treatment and increases in severity during the treatment period and until 7 days after the last drug date, then this event should also be considered as a TEAE. Major adverse cardiovascular events (MACEs, defined as all cardiovascular deaths, non-fatal myocardial infarctions and non-fatal strokes) are considered treatment-emergent until 30 calendar days after the last dose of trial product.

TEAEs are summarised descriptively, whereas non-TEAEs are presented in listings. TEAE data will be displayed in terms of the number of subjects with at least one event (N), the percentage of

subjects with at least one event (%), the number of events (E) and the event rate per 100 years of exposure (R).

Summaries of TEAEs and of serious TEAEs will be presented as an overview including all AEs, AEs by seriousness, AEs by severity, AEs by relation to treatment, technical complaint AEs and AEs by outcome (including deaths).

Furthermore, summary tables based on system organ class and preferred terms are made for:

- All TEAEs
- TEAEs leading to withdrawal
- Serious TEAEs
- Possibly or probably related TEAEs
- Severe, moderate and mild TEAEs
- TEAEs reported by safety areas of interest
- TEAEs with preferred term that are experienced by at least 5% of the subjects in any treatment arm or by at least 5% of all subjects

A listing for non-TEAEs with onset date before the first day of exposure to randomised treatment will be presented. A listing will also be presented for non-TEAEs collected after the treatment emergent period according to the definition of TEAE.

Classification of Hypoglycaemia

Treatment emergent: hypoglycaemic episodes will be defined as treatment emergent if the onset of the episode occurs on or after the first day of trial product administration, and no later than 7 days after the last day on trial product.

Nocturnal hypoglycaemic episodes: are episodes with time of onset between 00:01 and 05.59 both inclusive.

[figure not shown]
Hypoglycaemic episodes are classified according to the Novo Nordisk classification of hypoglycaemia (see [Figure 2-1](#)) and the ADA classification of hypoglycaemia (see [Figure 2-2](#)).

Novo Nordisk classification of hypoglycaemia

In normal physiology, symptoms of hypoglycaemia occur below a plasma glucose level of 3.1 mmol/L.⁵ Therefore, Novo Nordisk has included hypoglycaemia with plasma glucose levels below this cut-off point in the definition of BG confirmed hypoglycaemia.

Novo Nordisk uses the following classification (see [Figure 2-1](#)) in addition to the ADA classification (see [Figure 2-2](#)):

- Severe or BG confirmed symptomatic hypoglycaemia: An episode that is severe according to the ADA classification⁶ or BG confirmed by a plasma glucose value <3.1 mmol/L **with** symptoms consistent with hypoglycaemia.
- Severe or BG confirmed hypoglycaemia: An episode that is severe according to the ADA classification⁶ or BG confirmed by a plasma glucose value <3.1 mmol/L **with or without** symptoms consistent with hypoglycaemia.

[figure not shown]
Note: Glucose measurements are performed with capillary blood calibrated to plasma equivalent glucose values

BG: blood glucose PG: plasma glucose SMPG: Self-measured plasma glucose

Figure 2–1 Novo Nordisk classification of hypoglycaemia

ADA classification of hypoglycaemia⁶

- Severe hypoglycaemia: An episode requiring assistance of another person to actively administer carbohydrate, glucagon, or take other corrective actions. Plasma glucose concentrations may not be available during an event, but neurological recovery following the return of plasma glucose to normal is considered sufficient evidence that the event was induced by a low plasma glucose concentration.
- Asymptomatic hypoglycaemia: An episode not accompanied by typical symptoms of hypoglycaemia, but with a measured plasma glucose concentration ≤ 3.9 mmol/L.
- Documented symptomatic hypoglycaemia: An episode during which typical symptoms of hypoglycaemia are accompanied by a measured plasma glucose concentration ≤ 3.9 mmol/L.
- Pseudo-hypoglycaemia: An episode during which the person with diabetes reports any of the typical symptoms of hypoglycaemia with a measured plasma glucose concentration > 3.9 mmol/L but approaching that level.
- Probable symptomatic hypoglycaemia: An episode during which symptoms of hypoglycaemia are not accompanied by a plasma glucose determination but that was presumably caused by a plasma glucose concentration ≤ 3.9 mmol/L.

Note: Glucose measurements are performed with capillary blood calibrated to plasma equivalent glucose values

PG: plasma glucose SMPG: Self-measured plasma glucose

Figure 2–2 ADA classification of hypoglycaemia

Data on treatment emergent hypoglycaemic episodes are presented in terms of the number of subjects with at least one event (N), the percentage of subjects with at least one event (%), the number of events (E) and the event rate per 100 years (R).

Separate summaries are made for severe or BG confirmed hypoglycaemic episodes, severe or BG confirmed symptomatic hypoglycaemic episodes, nocturnal severe or BG confirmed hypoglycaemic episodes, nocturnal severe or BG confirmed symptomatic hypoglycaemic episodes and the ADA classification of hypoglycaemia.

The number of hypoglycaemic episodes during 26 weeks of treatment will be analysed separately for each endpoint using a negative binomial regression model with a log-link function and the logarithm of the time period in which a hypoglycaemic episode is considered treatment emergent as offset. The model will include treatment and previous OAD treatment at fixed factors.

Pulse

Change from baseline in pulse after 26 weeks of treatment will be analysed using the standard ANCOVA model.

Systolic and diastolic blood pressure

Change from baseline in systolic and diastolic blood pressure after 26 weeks of treatment will be analysed using the standard ANCOVA model.

Clinical evaluations (physical examination, eye examination and ECG)

Eye examination (dilated funduscopy/fundus photography) and ECG findings will be summarised descriptively, including:

- Summaries
- The change from baseline after 26 weeks of treatment

Any clinically significant deterioration of a pre-existing condition after the screening visit, as well as any new clinically significant findings will be recorded as adverse events.

Laboratory assessments

All laboratory parameters will be summarised descriptively. The following tables will be presented based on both observed and LOCF imputed data:

- Shift tables from baseline to after 26 weeks of treatment.
- Proportion of subjects with measurements outside reference range by treatment and week.

Laboratory values for lipase, amylase and calcitonin will be presented graphically as box plots by treatment and week.

For each laboratory parameter, individual values outside the reference ranges (abnormal values) will be listed.

For lipase and amylase the following rule applies in the evaluation of the result:

- If the amylase or lipase baseline (at screening) value is $> 3 \times \text{UNR}$ the information will be recorded as medical history for that subject.

Calcitonin

The purpose of the calcitonin analysis is to evaluate longitudinal changes in calcitonin, with main focus on subjects who develop persistently high levels of calcitonin during the trial.

Calcitonin will be displayed in terms of the number of subjects (N), the percentage of subjects (%) and the event rate per 100 years of exposure (R). The following criteria are defined for tabulations:

- **Persistent (all post baseline measurements)**
 - From $< \text{UNR}$ to persistently $\geq \text{UNR}$
 - From $< \text{UNR}$ to persistently $\geq 1.5 \text{ UNR}$
 - From $< \text{UNR}$ to persistently $\geq 20 \text{ ng/L}$
 - From $< \text{UNR}$ to persistently $\geq 50 \text{ ng/L}$
 - From $< 20 \text{ ng/L}$ to persistently $\geq 20 \text{ ng/L}$
 - From $< 50 \text{ ng/L}$ to persistently $\geq 50 \text{ ng/L}$
- **Incidental (at least one post baseline measurements)**
 - From $< \text{UNR}$ to $\geq \text{UNR}$
 - From $< \text{UNR}$ to $\geq 1.5 \text{ UNR}$
 - From $< \text{UNR}$ to $\geq 20 \text{ ng/L}$
 - From $< \text{UNR}$ to $\geq 50 \text{ ng/L}$
 - From $< 20 \text{ ng/L}$ to $\geq 20 \text{ ng/L}$
 - From $< 50 \text{ ng/L}$ to $\geq 50 \text{ ng/L}$

The distribution of all calcitonin measurements across treatment groups and time will be shown with box plots and corresponding cumulative plots for actual levels of calcitonin and change from baseline. The plots will be presented by treatment group at EOT using LOCF imputed values and within treatment group by week. Plots will be done by each gender, separately.

Summaries tables of calcitonin continuous measurements, will include number and percentage of observations $<$ and \geq LLOQ, minimum, Q25, median, Q75 and maximum. Summaries will be presented for all subjects and by gender.

Longitudinal changes for subjects with calcitonin levels ≥ 20 ng/l will be plotted (longitudinal plots). The plots will be done by treatment and gender. They will be done for subjects in the persistent and incidental categories, separately.

A listing of subjects with at least one post baseline value ≥ 20 ng/l will be done. The listing will include age, gender, calcitonin measurements over time and AE history (including preferred term, onset and stop dates).

Urinalysis

Categorical urinalysis parameters will be summarised descriptively by:

- Shift from baseline to EOT (using the number of subjects in the different categories).
- Subjects with at least one post baseline measurement outside reference range will be listed.

Insulin and GLP-1 antibodies

Insulin antibodies (IDeg specific, cross-reacting to human insulin and total) will be summarised with arithmetic mean, standard deviation (SD), median, and minimum and maximum value by treatment and treatment week, and their mean over time will be plotted. Correlations will be explored graphically as follows. Insulin antibodies (IDeg specific, cross-reacting to human insulin and total) will be plotted against HbA_{1c} after 26 weeks, HbA_{1c} change from baseline after 26 weeks, and dose after 26 weeks. Change from baseline to FU1 in insulin antibodies (IDeg specific, cross-reacting to human insulin and total) will be plotted against HbA_{1c} after 26 weeks, HbA_{1c} change from baseline after 26 weeks, and dose after 26 weeks.

GLP-1 antibodies (liraglutide specific, cross-reacting to native GLP-1, liraglutide *in vitro* neutralising and *in vitro* neutralising to native GLP-1) will be summarised by number of subjects (N) and percentage of subjects (%) with positive and negative samples.

